1. BACKGROUND

1.1 Can Chinese Herbs help in the treatment of Lung Cancer?

Lung cancer is the one of the most commonly occurring cancer and in 2012 there were an estimated 1.8 million new cases worldwide, representing 12.9% of all new cancers. Lung cancer is also the most common cause of death from cancer, with 1.59 million deaths (19.4% of total deaths; GLOBOCAN 2012) [1]. Despite advances in the design and administration of anti-cancer therapies over recent years, the majority of patients with non-small cell lung cancer (NSCLC) first present with advanced, inoperable disease and for these patients their overall 5-year survival rate is 2-4% and the median survival for stage IV (metastatic) disease is only 5-7 months [2]. In addition to their very poor chances of cure or extended survival, patients with advanced NSCLC frequently suffer a range of different symptoms related to both their disease and its treatment [3-6]. As a result there is a pressing need to develop more effective anti-cancer therapies and an imperative to enhance the effects of existing treatments and alleviate symptoms more effectively.

One type of complementary medical treatment with the potential to improve some outcomes in lung cancer is Traditional Chinese Medicine (TCM), in particular the use of carefully selected combinations of Chinese herbs (CH). Increasing numbers of patients with cancer are using complementary medicine, including CH, and evidence is accumulating from a growing number of laboratory studies and clinical trials, that CH may exert beneficial effects for cancer patients in the following ways:

- (i) Through direct anti-cancer effects: Studies have suggested CH has potential anti-cancer effects by inhibiting tumor cell division, increasing tumor cell death [7-16].
- (ii) Through enhancing potency and decreasing toxicity of standard anti-cancer treatment [17-27].

(iii) Through reduction in symptoms and improvement in general condition and quality of life [28-34].

The current proposal is a feasibility and acceptability study to establish the necessary groundwork for more detailed investigations into the role of CH in reducing symptoms and improving quality of life in NSCLC patients at the JGH. A standardized and easily administered form of CH will be used, incorporating a carefully selected combination of herbs designed to alleviate a range of common symptoms suffered by patients with advanced NSCLC.

1.2 Studies of use of CH in treatment of Cancer

Results of specific studies

There have been several clinical studies focused on the use of CH in the treatment of patients with a range of different cancers. Study designs vary from observational to three-arm double-blind trials and limited number of well designed randomized controlled trials (RCT) [25, 26, 28, 35]. There is considerable evidence that CH can lead to measurable improvements in symptoms and quality of life (QOL) [36-40]. For example a double-blind placebo-controlled trial by Mok et al [24] demonstrated that CH had a significant effect on the control of chemotherapy-associated nausea in patients with early-stage breast or colon cancers, but no parallel reduction in chemotherapy-related hematologic toxicity. In contrast a randomized, placebo-controlled trial in ovarian cancer patients (all stages) by Chan et al. [41] showed that the CH reduced cytokine levels and lessened the falls in lymphocyte count without any change in QOL. Indeed the role of CH to reduce leucopenia during chemotherapy has recently been the subject of an extensive literature review [42]. This review analysed 83 randomised controlled trials involving over 8,000 patients with a range of different cancers, CH formulations and chemotherapy treatments. They concluded that there was evidence of a beneficial effect of CH on leucocyte count and no reports of adverse events. However, the authors cautioned that the majority of these RCTs had a high risk of bias in answering the primary research question [42].

In lung cancer patients the literature suggests that combined treatment with chemotherapy and CH can improve survival rates, immediate tumor response, performance status and QOL for those with locally advanced and metastatic disease [43-45]. In a randomized controlled trial (RCT) of 61 patients with stage 3B/4 non-small-cell lung cancer the CH (Sheng-mai Injection (Table 1) in combination with Gu-

Study of Chinese herbs and lung cancer patients

Principal Investigator: [name]

jin Granule) given in addition to chemotherapy (Navelbine and Cisplatin) improved median survival time (13 mo vs 9 mo, P=0.014) and the response rate increased to 48.5% (16/33), compared to 32.2% (9/28) in controls treated with the same chemotherapy alone(P=0.04) [46]. In another clinical trial using Shenqi-fuzheng (Table 1) injection (Lizhu Co., China) in 232 advanced NSCLC patients showed that CH significantly improved the response rate and QOL of lung cancer patients [47]. Furthermore, a randomized controlled trial using the Feiji Recipe (Table 1) CH treatment enhanced the clinical therapeutic efficacy and alleviated side-effects of chemotherapy [40] and improved many domains of QOL [48]. More recently, Liang et al. [49] used RCT to examine the effect of CH (modified Shu Yu Wan formula) on QoL and response rate to treatment and treatment toxicity in advanced NSCLC patients receiving platinum-based chemotherapy. This study demonstrated significant beneficial effect of CH on QOL and significantly less chemotherapy-related toxicity.

Table 1 CH recipes used in the above mentioned clinical trials

Shengmai recipe		Shenqi-fuzheng recipe		Feiji recipe	
Ingredients	Dose	Ingredients	Dose	Ingredients	Dose
RenShen	3-15g	Dang Shen	6-30g	Sheng Di Huang	30g
Dang Shen	(15-45g)	RenShen	1-9g	Chi Shao	15g
Xi Yang Shen	(15-45g)	Fu Ling	9-18g	Huang Qin	12g
Mai Men Dong	5-30g	Dan Shen	3-30g	Dang Gui	12 g
Wu Wei Zi	2-6g	Chi Shao	4.5-15g	Fu Ling	15g
		Qing Pi	3-10g	Hong Hua	10g
		Chen Pi	3-9g	Gan Cao	9g
		Zhi Ban Xia	3-14g	Sheng Jiang	30g
		Gan Cao	3-30g		

The results above provide support for the concept that integrating CH with standard chemotherapy for lung cancer patients may be beneficial. Furthermore there are additional data for positive effects of other CH recipes as adjunctive treatment during radiotherapy. Thus Dixiong Decoction [50], Liangxue Jiedu Huoxue Decoction [51], and Shenqi Fuzheng injection [52] reduced radiation pneumonitis and improved clinical radiographic physiologic dyspnea scores and the Radiation Therapy Oncology Group (RTOG) grading score, in groups of NSCLC patients undergoing radiotherapy treatment.

Results of systematic reviews and clinical guidelines

In recent years several systematic reviews have summarized the literature on the results of around 24 clinical trials using CH in NSCLC [18, 35, 53-55]. These reviews concur that CH has some advantages in NSCLC patients as an adjuvant to chemotherapy for treatment of non-small cell lung cancer to improve quality of life and improve toxicity of chemotherapy. However, the broad range and heterogeneity of CH interventions used and the outcomes assessed still make it challenging to draw firm conclusions to guide day-to-day practice.

In Western countries, such as the United States, Australia, Canada, and members of the European Union, the popular use of herbal medicine has led to establishment of research funding agencies such as the U.S. National Institutes of Health (NIH) National Center for Complementary and Alternative Medicine (NCCAM; <http://nccam.nih.gov/>), and the Australian National Institute of Complementary Medicine (NICM; <http://www.nicm.edu.au>). As a result of these developments, the issue of integration of herbal therapy into modern medicine has been the subject of ongoing international discussions in the last few years in order to develop some guidance for use of CAM [56-59].

To date, three international guidelines have been published on the use of CAM in oncology (refs 58, 55, 59) but only one has focused specifically on lung cancer. In 2007 the American College of Chest Physicians (ACCP) evidence-based clinical practice guidelines published Complementary Therapies and Integrative Oncology in Lung Cancer [60]. This recommended the use of CH to treat the symptoms associated with cancer and its mainstream treatments, but only in the context of clinical trials. At that time the ACCP felt this should only be offered to patients who were no longer on active treatments [60] (Grade 1C recommendation: absence of directly applicable studies of good quality).

Evidently, the literature on the use of CH in treatment of NSCLC has expanded greatly over the seven years since the ACCP statement was published. Furthermore, improvements in the delivery of

cytotoxic chemotherapies and the advent of targeted treatments for lung cancer that are easier for patients to tolerate, has meant that an increasing proportion of patients including those with poor performance status are now being offered some anti-cancer treatment. Unfortunately, restricting the use of CH in NSCLC, to those who are no longer on active treatment will now select a very small group of patients with poor prognosis and means that the potential to confirm any effect of CH in alleviating cancer treatment-related symptoms is excluded. Furthermore it is notable that as of June 2014, 81 clinical trials with Chinese herbs are registered with the U.S. National Institutes of Health [59, 61]. Three of 81 trials are in lung cancer patients, two of which are using CH in combination with other chemotherapy:

- Clinical Study of Chemotherapy Combined With Chinese Medicine on Survival Affect of Elderly Patients With Lung Cancer (NCT01780181)
- Efficacy Study of Chinese Medicine Plus EGFR-TKI Versus EGFR-TKI in Advanced Pulmonary Adenocarcinoma (NCT01745302)
- Multi-center randomized double-blind controlled study of chemotherapy combined with or without traditional Chinese medicine on quality of life of postoperative non-small cell lung cancer patients (NCT01441752)

The patient perspective

The use of CH among cancer patients is growing and a recent cohort study with 453 cancer patients revealed that the percentage of patients using CH in combination with conventional treatment was as high as 77% [62]. For these patients CH was thought to have an important role in reducing therapy-associated toxicity, reducing cancer-related symptoms, supporting the immune system or even for its direct anti-cancer effects [63]. Reports from patients enrolled in studies of seven different cancer types, including lung cancer perceived CH to be an effective and harmless therapy. Subjects believed that conducting clinical research would be crucial for the recognition and dissemination of CH in Western countries [64]. A semi-structured interview of 12 lung cancer patients from JGH was conducted to explore their expectations and beliefs about complementary and alternative medicine including CH [65]. Positive beliefs and expectations were observed in all participants. Patients expressed four main beliefs that supported the use of CAM: maintaining a sense of control, preferring natural products or methods, valuing relationships with CAM providers, and being open to trying different strategies. Finally we have informal testimony from professionals at the Peter Brojde Centre at the JGH that confirms at least 12 recent patients with lung cancer used CH for the reasons stated above and most, if

not all, did so without declaring this to their oncologists. Overall this underlines a strong interest in CH amongst many patients with cancer, including lung cancer, and suggests that we should actively engage with patients on this subject and study the role of CH in clinical practice. In this way we will be better able to address the many questions and uncertainties about the potential benefits and risks of CH for our patients.

1.3 Clinical Safety of Chinese herbs

There are many areas of uncertainty and legitimate concern in trying to predict the potential toxicity of CH formulas such as the one proposed in clinical populations. We have identified the following general types of concerns and have addressed each one as it pertains to the proposed CH study at the Peter Brojde Lung Cancer Centre below:

- A. The inherent variability in chemical composition of herbs due to cultivation conditions and different geographic sources. **Response:** The source company for the herbs in this study (BEMA) obtain their botanicals from reputable farms in Taiwan (San Ten Pharmaceutical Company) and the Certificate of Analysis are provided (Appendix 1)
- B. The possibility of contamination with undeclared potentially toxic ingredients including heavy metals (arsenic, cadmium, lead and mercury) or microbial contamination (e.g. *E. coli*, *Salmonellaspp*, *Staphylococcus aureus*). **Response:** Each component has been independently tested at San Ten pharmaceuticals to confirm purity and absence of contamination and certificates confirming this are attached (Appendix 2)
- C. The difficulty accurately predicting safety and efficacy of individual ingredients from CH when the only robust quantitative data available is from pre-clinical experiments using doses that are frequently far higher than those achievable in humans. **Response:** The components of the CH formula we plan to use have been used for therapeutic benefit for several hundred years, and continue to be used to treat cancer patients in China. Community studies of reported side-effects from over-the-counter i.e. unsupervised, CH use [66] most commonly (<10%) include minor side effects such as allergic reactions (e.g. erythema, itching), dizziness and gastro-intestinal symptoms (e.g. diarrhea, stomach ache and cramping). Other rare (<1%) reported side-effects of individual herbs at very high doses include: several weeks or months' use of higher doses (e.g. >600 mg/day) of Licorice can cause suppression of the renin-aldosterone axis

leading to hypertension and hypokalemia [67]; Increased risk of bleeding: dong quai (angelica senesis) at the dose of 4.5 g daily due to antiplatelet activity: concurrent use of anticoagulants is not recommended [68]; Neurological and psychiatric toxicity: Panax ginseng may cause insomnia, mania and/or euphoria when used in a dose >2 g daily over prolonged time (3 months) [69, 70]. The toxicities reported argue for supervised use of CH in clinical studies to monitor symptoms and parameters such as blood pressure.

D. There is genuine difficulty in predicting potential clinically important interactions between CH and other chemicals or biomolecules at physiologically relevant concentrations. This in turn raises the possibility that for patients receiving potentially highly toxic treatments such as chemotherapy, CH may increase the risk of toxicity. Additionally, for patients being treated with curative intent there is potential that any additional treatment such as CH may reduce rather than enhance any anti-cancer effect and jeopardise survival. **Response:** In recent years there has been a rapid increase in the number of published studies using CH in cancer patients, including many studies using CH at the same time as chemotherapy. Not one of these studies has reported an increase in symptoms or adverse effects due to CH despite use in a variety of different patient groups, and many claim that CH enhances rather than reduces anti-cancer treatment effects. This protocol is deliberately designed to test CH in stage IV lung cancer patients, where anti-cancer treatment is intended to reduce or control symptoms and improve quality rather than extend life. To be able to better identify if CH are causing, rather than reducing toxicity for those on chemotherapy, we will start CH only in patients who have no chemotherapy planned or in those starting chemotherapy CH will be initiated only if they are clinically stable and have completed at least the first cycle of chemotherapy. Furthermore, to reduce the potential for other toxicities, patients will be instructed not to take other over-the-counter CH.

1.4 Rationale, composition and safety data for the of the study formula - Shu Yu Wan (Chinese Yam Pill) formula

The basis for the formula chosen is the “Eight treasure deconcoction” (Protocol Table 2: 1-8) that is used to improve energy and combat fatigue in otherwise healthy individuals. This fundamental formula is represented in the majority of deconcoctions studied in the recent review by Ma et al [ref]. In the context of other diseases the Eight Treasures combination is not thought to be strong enough and the remaining 13 herbs are added for their anticipated supplementary effects in treating symptoms in

the context of lung cancer. These include herbs to help with lung symptoms such as cough (10,11,15) and dry mouth (17), poor appetite and early satiety (13, 14,20, 21), emotional stress (18) and to strengthen the individual's natural defences (12, 19,22,23) in the face of severe illness. The classical Shu Yu Wan formula dates back to the late Han dynasty c. 220 AD and includes 21 herbs. This formula has been used for hundreds of years as a treatment for severe illness-induced fatigue and weakness. However, two of the classical ingredients (Da Dou Huang, Bai Lan) are not approved in the NHPD list and have been substituted with appropriately selected additional herbs that are on NHPD approved list (Table 2:15,20,22,23). In Traditional Chinese Medicine there is considerable scope for individual practitioners to choose different herbs from each botanical family to treat different patients with the same symptom. Interestingly, another group in China has published on a study of their own version of a modified Shu Yu Wan formula [49] and its use for improving QoL for patients with Non-small cell lung cancer. Liang et al's formula included 25 herbs, of which 21 are exactly the same as the ones chosen for the Shu Yu Wan formula selected for our study.

In choosing the CH used in this study, the aim was to identify a balanced combination that would be generally applicable and effective in reducing symptoms for patients with advanced lung cancer. As described above this study will use the modified **Shu Yu Wan** formula with 23 different herbs (Table 2). In addition it was our express intention to include the botanicals that are most likely to improve symptoms and quality of life in patients with advanced lung cancer and not to include botanicals because of any potential anti-cancer activity. In contrast to the usual TCM practice, we will use a standardized formula suitable for all patients, rather than an individualized CH prescription with only selected components.

All the components of the modified **Shu Yu Wan in this protocol** have been approved by Health Canada and listed as acceptable medical ingredients[71, 72], and were the subject of in-depth analysis process as part of a prior CIHR grant application to determine efficacy and safety of CH in cancer patients [73]. Although some mild side effects have been reported when single herbs from the **Shu Yu Wan formula** have been used in doses far exceeding that in our formula, none of the component of this formula are listed as a herbals to be used with caution in *Herb Contraindications and Drug Interactions, 4th edition*[74]. Furthermore most of the ingredients have a high therapeutic index and are unlikely to cause toxicity even used in considerable excess. In general, use of combinations of smaller quantities of herbs seems to cause fewer adverse reactions than larger doses of single herbs, and

combining 23 herbs in one formula allows the use of smaller doses of herbs with synergistic beneficial effects.

More details of individual potential herbal-drug interactions of the components the modified Shu Yu Wan formula is presented in the Appendix 3. It should be noted that most of the data on toxicities reported here come from studies cited in Chinese Herbology textbooks [75].

The closely related modified Shu Yu Wan formula used in another study of advanced lung cancer patient receiving chemotherapy led to significantly fewer adverse reaction when compared to chemotherapy alone [49]. However we note that most of the herbs are metabolized in the liver and that there is potential for reversible hepatotoxicity at high doses or in susceptible patients [76]. This general point will be taken into account in patient selection for the current study. Thus, we propose to exclude patients with abnormal liver function or those taking drugs with long half-lives namely anti-convulsants, anticoagulants, or lithium where minor changes in drug metabolism may lead to delayed and potentially serious sequelae.

2. OBJECTIVES

2.1 Primary objectives:

- To assess the acceptability and feasibility of conducting a 6-week intervention with a standard CH formula designed to treat symptoms commonly experienced by patients with advanced NSCLC.

Acceptability will be assessed using the following questions at the end of the study:

- **Indirectly** from adherence and feasibility (see below)
- **Directly** from responses to the following questions:
 - i) “*Was the Chinese Herb treatment used in this study easy to take?*” Yes / No
 - ii) “*If you experienced any problems or side effects taking the Chinese Herb treatment used in this study, please tell us what these were.*” (Free text)
 - iii) “*If it was available, would you be willing to take the Chinese Herb treatment used in this study again?*” Yes / No / Don’t know

Feasibility will be assessed using the following indices:

- Willingness to participate: proportion of subjects enrolled from number of patients approached .
- Completion rates: proportion of enrolled subjects who completed study (including final assessment) (threshold for positive study: 60%)
- Adherence rates: Proportion of doses taken of number prescribed (threshold for positive study: 66%)

2.2 Secondary objectives:

- a) Assess the magnitude of the patients' quality of life response and symptoms change after the 6 -week intervention compared to baseline.
- b) Estimate an appropriate sample size for the fully implemented study

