3.2 Sample size

15 patients with advanced non- small- cell- lung cancer will be recruited over a 12- month period at a rate of 1-2 patients per month to receive CH plus standard care. We intend to approach 80 patients from a pool of 200 active advanced NSCLC patients who meet eligibility criteria. Estimated length of the study would be about 18 months.

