4.4 Method of Treatment

After written informed consent has been obtained and eligibility has been established the patient will be asked to complete FACT-L and ESAS questionnaires. The patients will be offered the choice of taking the CH formula in capsules or sachets and given instructions about recommendations to improve palatability. The formula should be taken with meals 3 times a day (each dose is either 1 sachet or 4 capsules) for six-weeks. Patient will be instructed to complete a diary each day to confirm adherence to treatment and to indicate the reason(s) that any doses were missed or treatment was stopped. A two-week supply of the CH capsules/sachets will be dispensed to patient at the start of the study. Every two weeks thereafter diaries will be collected/checked with the patient and a new diary dispensed with the next two-week supply of formula. The written instructions about dosage, frequency, dosage timing and what to do in the event of an adverse reaction will be given to patients.

Study of Chinese herbs and lung cancer patients

Principal Investigator: [name]

Patients will be allowed to maintain their concomitant medications during the trial with exception of over-the-counter herbal supplements.

4.5 Withdrawal.

Patients may withdraw at any time during the trial for the following reasons:

1. Patient no longer wishes to participate
2. The patient's doctor makes the decision to withdraw the patient if any side effects are suspected.
3. An allergic response or adverse reaction to the Chinese herbs
4. A change in clinical status necessitating emergency admission for treatment
5. Evidence of worsening liver function or need to start medication included in the exclusion criteria.
6. Reduction of chemotherapy dose due to Grade 3 toxicity

In case if participation terminated prematurely, patient will still be asked to attend for the end of the study visit.

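### Does the 66% adherence criterion need a written rule for doses after an early stop, and for combining it with the 60% completion threshold?

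*Protocol*

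**What the plan says.** Protocol section 2.1 lists three feasibility indices, and two of them carry a pass mark. Completion is the "proportion of enrolled subjects who completed study (including final assessment) (threshold for positive study: 60" per cent). Adherence is "Adherence rates: Proportion of doses taken of number prescribed (threshold for positive study: 66" per cent). The third, willingness to participate, has no mark.

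Section 4.4 sets the regimen: "The formula should be taken with meals 3 times a day (each dose is either 1 sachet or 4 capsules) for six-weeks". Supplies are issued in instalments: "A two-week supply of the CH capsules/sachets will be dispensed to patient at the start of the study", with further two-week supplies at later visits. Patients keep a daily diary and are asked "to indicate the reason(s) that any doses were missed or treatment was stopped".

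Section 4.5 lists reasons for withdrawal. Some are the patient's own choice and some are medical, among them "Reduction of chemotherapy dose due to Grade 3 toxicity". It adds: "In case if participation terminated prematurely, patient will still be asked to attend for the end of the study visit".

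On numbers, section 3.2 states that "15 patients with advanced non- small- cell- lung cancer will be recruited over a 12- month period". The SAP plans descriptive summaries (percentages, means with standard deviations, proportions). It names neither adherence, completion nor either mark.

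**The concern.** Completion has a stated denominator, the enrolled subjects. Adherence has only the doses prescribed, with no patient set and no rule for a patient who stops. Someone withdrawn by the doctor in week 2 is arguably no longer prescribed anything, so the denominator could be the whole six-week course or only the doses due up to the stop. On the second reading a patient who leaves adds no missed doses, and dropout cannot lower the figure.

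The plan also does not say outright whether a positive study needs both marks or only one. Since these are the only two pass marks for the primary objective, the same diaries might be called a pass or a fail, and the choice could be made after the data are seen.

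**Working it through.** There is no planned figure to reproduce: neither the 66% mark nor the sample size of 15 is derived in the documents. The check is how far the two readings can differ.

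**Inputs from the protocol.** 3 doses a day for 42 days (section 4.4); 15 patients (section 3.2); marks of 60% and 66% (section 2.1).

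- Full course per patient: 3 x 42 = 126 doses. For 15 patients: 15 x 126 = 1,890.
- Doses due for a patient who stops at day 14: 3 x 14 = 42.
- Smallest passing completion count: 0.60 x 15 = 9, so up to 6 non-completers are tolerated.

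**Assumed inputs** (the documents give no expected rates): number of early stoppers k, stop day d, and a common on-herb adherence a.

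**Illustration:** k = 6, d = 14, a = 85%.

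- Doses due up to stopping: 9 x 126 + 6 x 42 = 1,134 + 252 = 1,386.
- Doses taken: 0.85 x 1,386 = 1,178.1.
- Full-course adherence: 1,178.1 / 1,890 = 62.3%, below 66%.
- Adherence up to stopping: 1,178.1 / 1,386 = 85.0%, above 66%.
- Completion: 9/15 = 60%, just met. On the full-course reading the study is then negative if both marks are needed and positive if one is enough.

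**Range of disagreement.** Full-course adherence equals a x [1 - (k/15)(1 - d/42)], while adherence up to stopping equals a. The readings disagree when a is at least 0.66 but below 0.66 / [1 - (k/15)(1 - d/42)].

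| Stoppers k | Stop day d | Bracket | Readings disagree for a from 66% to just under |
|---|---|---|---|
| 6 | 7 | 0.6667 | 99.0% |
| 6 | 14 | 0.7333 | 90.0% |
| 6 | 28 | 0.8667 | 76.2% |
| 3 | 14 | 0.8667 | 76.2% |
| 3 | 28 | 0.9333 | 70.7% |
| 1 | 14 | 0.9556 | 69.1% |

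The gap is wide only when dropout is near the tolerated limit and early. The upper limits in the last column are also the on-herb adherence needed to pass if the full-course figure governs.

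**What the wording supports.**

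- *Denominator.* Section 2.1 speaks of doses prescribed. Section 4.4 gives the regimen for six weeks and, like Table 3, uses a different word, dispensed, for the two-week supplies. How the supply is issued does not redefine the prescription, so 126 doses is the natural denominator.
- *Combination.* Each index has its own mark for a positive study. Nothing suggests that meeting one excuses missing the other.
- *Completers.* Section 2.1 makes the final assessment part of completing, not a substitute for it, and section 5.4 places the end of the study at six weeks. A patient who stopped early but attends the last visit is already best read as a non-completer.

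**The case for a change.** The strongest case for a change is that these are pass marks for the primary objective, early stopping is foreseen, the SAP is silent, and a sentence or two would stop the denominator being picked after the result is known. It is correct that no sentence settles the count after a stop, and the arithmetic shows that the reading can decide the 66% mark when several patients leave early.

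The case weakens when one asks which rule to impose. Making the full-course figure govern puts every early stop into both indices. At the protocol's own minimum of 9 completers, it would need 90.0% on-herb adherence with day-14 stops and 99.0% with day-7 stops, which largely cancels the stated tolerance of 40% non-completion. It would also score withdrawals for emergency admission, worsening liver function or chemotherapy dose reduction as doses not taken, although section 2.1 uses adherence as an indirect measure of acceptability.

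The opposite choice, adherence while on the herbs beside completion over all enrolled, is not blind to dropout, because completion captures it against its own mark. Both are defensible. The diaries support either count, and the completion rate shows the dropout whichever is used.

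A related complaint is that no interval is planned. For 9/15 the exact (Clopper-Pearson) 95% interval is 32% to 84%, so precision is poor. But the marks in section 2.1 are set against observed proportions, and an interval would change no threshold decision.

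**Conclusion.** No change to the plan is needed. The gap is an unwritten definition that an analyst can fill sensibly from the protocol: 126 prescribed doses per patient, and both marks required. The main alternative is also sound, and fixing the full-course count as decisive would be a trade-off rather than a correction.

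The possible effect is not nil. It reaches 62.3% against 85.0% with 6 of 15 stopping at day 14 and 85% of doses taken on the herbs. With one such stopper it shrinks to a disagreement only between 66% and 69.1% on-herb adherence. These sizes rest on assumed stop days, stopper counts and a common on-herb adherence, none of which the documents give. In a 15-patient, single-group, descriptive feasibility study, stating the denominator beside the percentage is enough for a reader to judge the result.
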